7. COLLECTION OF STUDY VARIABLES

7.1 Recording of Data

All information will be recorded locally and entered into Case Report Forms (CRFs) on the web-based electronic data capture (EDC) system of the University of Michigan. Online access will be provided to each site by the Coordinating Center.

CRFs will be reviewed and source verified by the MSPM during annual monitoring visits and prior to and between visits. Discrepant, unusual and incomplete data will be queried by the MSPM. The investigator or study coordinator will be responsible for providing resolutions to the data queries, as appropriate. The investigator must ensure that all data queries are dealt with promptly.

The data submission schedule is as follows:

- At the time of registration
 - Subject entry into EDC
 - Subject Status
 - Demographics
- During study participation
 - All data should be entered online within 10 business days of data acquisition. Information on Serious Adverse Events must be entered within the reporting timeframe specified in Section 7.7 of the protocol.

All study information should be recorded in an appropriate source document (e.g. clinic chart).

7.2 Record Retention

The investigator will maintain adequate and accurate records to enable the conduct of the study to be fully documented and the study data to be subsequently verified. After study closure, the investigator will maintain all source documents and study-related documents. Records are to be retained and securely stored until the later of: (a) two (2) years following the date a New Drug Application is approved for the Study Drug that is the patient of the Clinical Trial; or (b) two (2) years after the Investigational New Drug Application for such Study Drug is terminated or withdrawn, or such longer period of time as may be required by Participant policies, applicable laws, rule or regulations.

7.3 Data and Safety Monitoring

This study will be monitored in accordance with the NCI approved University of Michigan Rogel Cancer Center Data and Safety Monitoring Plan, with oversight by the Rogel Cancer Center Data and Safety Monitoring Committee (DSMC).

The Sponsor Investigator (S-I)/Study Principal Investigator and/or the Project Manager/Delegate will review data and patient safety issues with participating sites per a defined quarterly meeting cadence. Depending on the protocol activity, the meeting cadence may be more frequent. This data review meeting may be achieved via a teleconference or another similar mechanism to discuss matters related to:

- Enrollment rate relative to expectations, characteristics of participants
- Safety of study participants (SAE reporting, unanticipated problems)
- Adherence to protocol (protocol deviations)
- Completeness, validity and integrity of study data
- Retention of study participants

Participating sites are required to ensure all pertinent data for the review period are available in the database at the time of the discussion.

Participating sites unable to participate in the data review meeting are required to provide written confirmation that their site has reviewed the relevant data and patient safety issues for the review period and their site's data are in alignment with the data reported in the database. Written confirmation is to be provided to the Project Manager/Delegate within the timeline requested to retain compliance with monitoring timelines.

Documentation of the teleconference or alternate mechanism utilized to review items above is to be retained in the Trial Master File.

The Project Manager/Delegate is responsible for collating the data from all participating sites and completing the Protocol Specific Data and Safety Monitoring Report (DSMR) form to document the data review meeting discussion.

The DSMR will be signed by the Sponsor-Investigator (S-I)/Study Principal Investigator or designated Co-Investigator and submitted to the DSMC on a quarterly basis for independent review.

7.4 Quality Assurance and Audits

The Data and Safety Monitoring Committee can request a 'for cause' quality assurance audit of the trial if the committee identifies a need for a more rigorous evaluation of study-related issues.

A regulatory authority (e.g. FDA) may also wish to conduct an inspection of the study, during its conduct or even after its completion. If an inspection has been requested by a regulatory authority, the site investigator must immediately inform the Coordinating Center that such a request has been made.

7.5 Clinical Monitoring Procedures

Clinical studies coordinated by The University of Michigan Rogel Cancer Center must be conducted in accordance with the ethical principles that are consistent with Good Clinical Practices (GCP) and in compliance with other applicable regulatory requirements.

This study will be monitored by a representative of the Coordinating Center of The University of Michigan Rogel Cancer Center. Monitoring visits will be made during the conduct of the study and at study close-out.

Prior to subject recruitment, a participating site will undergo a site initiation meeting to be conducted by the Coordinating Center. This will be done as an actual site visit; teleconference, videoconference, or web-based meeting after the site has been given access to the study database and assembled a study reference binder. The site's principal investigator and his/her study staff should make every effort in attending the site initiation meeting. Study-related questions or issues identified during the site initiation meeting will be followed-up by the appropriate The University of Michigan Rogel Cancer Center personnel until they have been answered and resolved.

Monitoring of this study will include both 'Centralized Monitoring', the review of source documents at the Coordinating Center and 'On-site Monitoring', an actual site visit. The first 'Centralized' visit should occur after the first subject enrolled completes Cycle 2. The study site will send the de-identified source documents to the Coordinating Center for monitoring. 'Centralized' monitoring may be requested by the Coordinating Center if an amendment requires changes to the protocol procedures. The site will send in pertinent de-identified source documents, as defined by the Coordinating Center for monitoring.

The first annual 'On-site' monitoring visit should occur after the first five study participants are enrolled or twelve months after a study opens, whichever occurs first. The annual visit may be conducted as a 'Centralized' visit if less than three subjects have enrolled at the study site. The type of visit is at the discretion of the Coordinating Center. At a minimum, a routine monitoring visit will be done at least once a year, or once during the course of the study if the study duration is less than 12 months. The purpose of these visits is to verify:

- Adherence to the protocol
- Completeness and accuracy of study data and samples collected
- Proper storage, dispensing and inventory of study medication
- Compliance with regulations

During a monitoring visit to a site, access to relevant hospital and clinical records must be given by the site investigator to the Coordinating Center representative conducting the monitoring visit to verify consistency of data collected on the CRFs with the original source data. While most patient cases will be selected from patients accrued since the previous monitoring visit, any patient case has the potential for review. At least one or more unannounced cases will be reviewed, if the total accruals warrant selection of unannounced cases.

The Coordinating Center expects the relevant investigational staff to be available to facilitate the conduct of the visit, that source documents are available at the time of the visit, and that a suitable environment will be provided for review of study-related documents. Any issues identified during these visits will be communicated to the site and are expected to be resolved by the site in a timely manner. For review of study-related documents at the Coordinating Center, the site will be required to ship or fax documents to be reviewed.

7.6 Efficacy

Response and progression will be evaluated in this study using a combination of the international criteria proposed by the RECIST Committee for measurable disease and the guidelines for prostate cancer endpoints developed by the Prostate Cancer Clinical Trials Working Group (PCWG3)[14] for bone metastasis.

Patients will need to be reevaluated for response according to the guidelines below.

7.6.1 PSA

Perform PSA testing at a minimum of 4-weeks intervals with the threshold PSA level at 1.0 ng/mL. To report PSA-based outcomes, PCWG3 recommends that the percent of change in PSA from baseline to 12 weeks (or earlier for those who discontinue therapy) and the maximum decline in PSA that occurs at any point after treatment be reported for each patient. PSA rise alone is insufficient to define progression within the study (see Section 7.6.7).

7.6.2 Response evaluation criteria in solid tumors (RECIST)

Response and progression will utilize the new international criteria proposed by the revised RECIST guideline (version 1.1) in combination with other metrics [15]. Changes in the largest diameter (unidimensional measurement) of the tumor lesions and the shortest diameter in the case of malignant lymph nodes are used in the RECIST criteria.

7.6.3 Definitions

Evaluable for toxicity. All patients will be evaluable for toxicity from the time of their first treatment with any drug.

Evaluable for progression-free survival. Only patients who begin treatment will be evaluable for progression-free survival.

Evaluable for objective response. A patient who receives at least one dose of treatment will be considered evaluable for objective response. A patient who does not have an assessment for response after starting treatment will be considered a non-responder and will be censored for progression at the time of removal from the study.

Evaluable Non-Target Disease Response. Patients who have lesions present at baseline that are evaluable but do not meet the definitions of measurable disease, begin treatment, and have had their disease re-evaluated will be considered evaluable for non-target disease. The response assessment is based on the presence, absence, or unequivocal progression of the lesions.

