5.7.2 Off study criteria

Patients can be taken off study at any time at their own request, or they may be withdrawn at the discretion of the investigator for safety, behavioral, administrative reasons or progression. The reason(s) for discontinuation from study will be documented and may include:

- Patient withdraws consent (termination of treatment and follow-up);
- Loss of ability to freely provide consent through imprisonment or involuntary incarceration for treatment;
- Patient is unable to comply with protocol requirements;
- Treating physician views continuation on the study would not be in the patient's best interest;
- Development of second malignancy (except for basal cell carcinoma or squamous cell carcinoma of the skin) that requires treatment, which would interfere with this study;
- Lost to Follow-up. If a research subject cannot be located to document survival after a period of 2 years, the subject may be considered "lost to follow-up." All attempts to contact the subject during the two years must be documented;

Termination of the study by The University of MichiganPatient completes protocol treatment and follow-up criteria

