10.1.2 Analysis of the secondary endpoints

- The response rate and 95% binomial confidence interval will be reported for DRDef patients.

The following endpoints will be reported for DRDef and DRPro patients separately

- Objective progression-free survival (combined radiographic and clinical progression-free survival) will be reported using Kaplan-Meier methods. This is measured from the date of treatment arm assignment until the specified tumor progression (assigned at the earliest observed time). Patients whose disease has not progressed at follow-up will be censored at the date when the last tumor assessment determined a lack of progression.
- Objective radiographic disease response rate is determined by the proportion of patients with measurable disease that have a response (CR+PR) according to RECIST v1.1. The proportion of responders will be reported with the corresponding 95% binomial confidence interval.
- PSA progression-free survival (PSA-PFS) will be reported as the composite of survival and duration of PSA control as defined by after a start of therapy from baseline to time of first PSA increase $\geq 25\%$ and ≥ 2 ng/mL above the nadir and confirmed by a second value at or beyond 4 weeks later. Kaplan-Meier methods will be used to report PSA-PFS.

- PSA response rate (≤ 0.2 ng/ml, 50% decline, 90% decline) proportions will be reported with corresponding 95% binomial confidence intervals. A waterfall plot of the best PSA response decline will be reported.
- Evaluate the qualitative and quantitative AE summaries will be reported by DNA repair status and organized by body system, frequency of occurrence, intensity (e.g. severity grade) and causality or attribution. Counts and proportions will be included. Treatment exposure will be summarized for all patients, including dose administration, number of cycles, dose modifications or delays and duration of therapy. Categorical variables will be reported using counts and frequencies. Continuous variables will be summarized using means or medians with the appropriate measure of variability.
- Duration of combined radiographic and PSA response will be reported using Kaplan-Meier methods.

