10.2 Analysis Populations

10.2.1 Response-to-treatment populations

All patients who meet eligibility criteria and receive at least one dose of study medication will be included in the main analysis of the response rate, even if there are major protocol deviations (e.g., incorrect treatment schedule or drug administration). Each patient will be assigned to one of the following categories for each response outcome:

TABLE 7: Categories for Response to Treatment

Category	Response
1	Complete response
2	Partial response
3	Stable disease
4	Progressive disease
5	Early death from malignant disease
6	Early death from toxicity
7	Early death from other causes

8	Unknown (not assessable/insufficient data)
---	--

NOTE: By arbitrary convention, category 8 designates unknown status in a clinical database. Patients in response categories 4 to 8 will be considered to have treatment failure (disease progression)

Conclusions are to be based on the population of all eligible patients who receive at least one dose of study medication. Subanalyses will be performed on various subsets of patients, such as those with no major protocol deviations, those who have at least one measure of response after starting treatment or those who continued in the study for the entire treatment period (i.e. did not withdraw prematurely). Sub-analysis will not serve as the basis for drawing conclusions concerning treatment's efficacy.

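### Objective PFS has two unreconciled censoring rules for a treated patient with no post-baseline assessment, and the Section 7.6.3 rule can keep an unscanned patient at risk past the first scan

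*Combined protocol and SAP*

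**What the plan says.** Section 7.6.3 ties PFS evaluability to starting treatment and nothing more: "Only patients who begin treatment will be evaluable for progression-free survival". Its paragraph on objective response then says that a treated patient with no assessment for response after starting "will be considered a non-responder and will be censored for progression at the time of removal from the study".

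Section 10.1.2, which specifies the Kaplan-Meier analysis of objective PFS, has a different rule: "Patients whose disease has not progressed at follow-up will be censored at the date when the last tumor assessment determined a lack of progression".

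Section 10.2.1 introduces Table 7 with "Each patient will be assigned to one of the following categories for each response outcome". Category 8 is for unknown or not assessable status. The note below the table reads "Patients in response categories 4 to 8 will be considered to have treatment failure (disease progression".

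Other provisions that bear on the point:

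- Section 2.2 counts radiographic progression, clinical decline and death as objective-PFS events, with time running from start of treatment. Sections 7.6.7.6 and 10.1.2 run time from assignment to a treatment arm.
- The study calendar (Section 5) schedules scans every 8 weeks, give or take one week, from C1D1. The baseline scan is at most 4 weeks before C1D1.
- Section 5.6.2 follows patients for 30 days after removal from treatment, or until death.
- Section 5.7.2 allows a subject to be classed as lost to follow-up "If a research subject cannot be located to document survival after a period of 2 years".

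**The concern.** Consider a patient who starts treatment, stops at week 6 and is never scanned on study. Section 7.6.3 gives him progression-free time up to removal from the study. Section 10.1.2, applied to his only scan, gives him none. The programmer has to choose, possibly after seeing the data.

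The 7.6.3 date is the weaker of the two. Removal from the study is not the end of treatment, so he can still be in the risk set at week 8, when scanned patients are first found to have progressed radiographically. He has no scan that could show the same. He enlarges the denominator at that drop, and the curve falls less than it should. Patients who leave before the first scan plausibly include those with early toxicity or decline, so the direction is favourable to the treatment.

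The Table 7 note adds a clash of words: it labels an unassessable patient as having disease progression, while 7.6.3 calls the same patient censored for progression.

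At stake is the objective-PFS curve in cohorts of 35 (DRPro) and 12 (DRDef), where a few patients can move it.

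**Working it through.** The documents give no PFS assumption and no expected number of unassessed patients, so there is no planned figure to reproduce. Median PFS, number unassessed and removal time below are assumptions.

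**One patient, last dose at week 6, never scanned**

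- Section 7.6.3: removal after the 30-day follow-up, 6 + 30/7 = 10.3, so censored at about week 10.
- Section 10.1.2: the only scan predates C1D1, so censored at time zero by convention, or undefined.
- Table 7 note: no PFS time or event date is given.

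**Cohort of n = 35 with k = 3 unassessed**

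Assume exponential PFS with a 16-week median, detected at the scans in weeks 8 and 16.

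- S(8) = 0.5^(8/16) = 0.707 and S(16) = 0.500.
- Expected progressions found at week 8 among the 32 assessed: 32 × (1 − 0.707) = 9.37.

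Expected 16-week Kaplan-Meier estimate:

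- Censored at time zero: S(16) = 50.0%.
- Censored at week 10: (1 − 9.37/35) × (0.500/0.707) = 0.732 × 0.707 = 51.8%.
- Removed at week 6: no scan-detected event has occurred, so the risk set at week 8 is 32, as with time-zero censoring: 50.0%.

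The gap between the two rules is (k/n) × (1 − S(8)) × S(16)/S(8) = (3/35) × 0.293 × 0.707 = 1.8 points. With k = 1 it is 0.6 points and with k = 5 it is 3.0 points. Simulation with 4,000 replicates gave 49.9% and 51.6% to 51.7%, which agrees. The sampling SD of the estimate is about √(0.5 × 0.5/32) = 9 points.

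Two further treatments of these patients bracket the result:

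- Counted as events at week 6: (32/35) × 0.500 = 45.7% (simulated 45.6%).
- Kept at risk to 2 years: (35 − 32 × 0.5)/35 = 19/35 = 54.3% (simulated 54.2%).

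**DRDef, n = 12, k = 1, assumed median 36 weeks**

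S(8) = 0.857 and S(16) = 0.735. The gap is (1/12) × 0.143 × (0.735/0.857) = 1.0 point, against an SD of about √(0.735 × 0.265/11) = 13 points.

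**A second set of assumptions at 24 weeks**

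Fixed progression times were placed on the protocol scan grid for 35 patients, with a median of 3 or 6 months, 1, 3 or 5 unassessed, and removal at week 6 or 10. The 24-week estimate differed by 0 to 0.02 between 7.6.3 and time-zero censoring. It differed by 0.008 to 0.095 between 7.6.3 and counting the patients as events at removal. For example, with a 6-month median, 3 unassessed and removal at week 10, the three values were 0.542, 0.531 (17/32) and 0.486 (17/35).

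**The case against.** The best defence is that the two sections do not conflict. A pre-treatment scan cannot establish absence of on-study progression, so 10.1.2 is silent on this patient and 7.6.3 is the specific rule that fills the gap. That reading is possible, but it does not rescue the rule: 7.6.3 still credits time with no scan behind it and can still carry the patient past week 8.

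The example patient may also fall outside 7.6.3. Response in Section 10.1.1 includes PSA, and the calendar draws PSA on day 1 of cycle 2 and at end of treatment, so a week-6 leaver would normally have a value. Whether PSA alone is an assessment for response is not stated. This stands, and the fix has to settle it.

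The time credited is not wholly unobserved. Clinical decline and death are events, and the calendar includes an end-of-treatment visit at 30 days. Early decline that meets the criteria is counted under the present text. This stands and limits the bias.

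Three stronger readings are tempting, and the documents do not support them:

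- A reader might infer three different PFS values, with Table 7 supplying an event. Table 7 classifies response outcomes, does not name PFS and gives no date. It reaches PFS only if its label is carried across.
- A reader might take the 2-year loss-to-follow-up period as the usual removal date. It is permissive wording for subjects who cannot be located; ordinary follow-up ends at 30 days.
- With the assumed median set at exactly 16 weeks, the estimated median can appear to move from 16 to 24 weeks between time-zero and week-10 censoring. That comes from placing the true median on a scan date. It did not appear at assumed medians of 13, 15, 17, 20 or 26 weeks.

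**Conclusion.** The point holds as a flaw in a stated rule, with a small effect. For a treated patient without post-baseline imaging, 7.6.3 and 10.1.2 lead to different censoring dates or, on the kinder reading, 7.6.3 alone applies and is a poor rule. Under the assumed inputs the 16-week DRPro estimate rises by about 2 points when removal is at week 10 and by nothing when removal precedes week 8. That is well inside sampling error. Larger gaps require the Table 7 label to be imported into PFS, or very late removal.

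The effect is confined to a descriptive secondary endpoint. No hypothesis, power statement or go/no-go rule uses PFS. The primary response rate is untouched, because 7.6.3 and 10.2.1 both leave this patient in the denominator as a non-responder.

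**What to change.** - In 7.6.3 and 10.1.2, state one rule: a treated patient with no post-baseline tumor (imaging) assessment is censored for objective PFS at day 1, unless clinical progression or death is documented, which is an event on its date. Keep the existing 10.1.2 rule for patients with at least one post-baseline scan.
- Use start of treatment as the single PFS origin in 2.2, 7.6.7.6 and 10.1.2, so that day 1 is time zero.
- State that a PSA value alone is not a tumor assessment for this rule.
- Limit the Table 7 note to non-response by deleting the bracketed disease-progression label for category 8.
- Report the number of unassessed patients per cohort, with one sensitivity curve counting them as events.

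The cost is wording in a few places and one extra curve. PFS may look slightly less favourable.

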7.6.4 Disease parameters

Measurable disease. Measurable lesions are defined as those that can be accurately measured in at least one dimension (longest diameter to be recorded) as >20 mm by chest x-ray, as >10 mm with CT scan, or >10 mm with CT scan, MRI, or calipers by clinical exam. All tumor measurements must be recorded in millimeters (or decimal fractions of centimeters).

Note: Tumor lesions that are situated in a previously irradiated area are not considered measurable.

Malignant lymph nodes. To be considered pathologically enlarged and measurable, a lymph node must be >15 mm in short axis when assessed by CT scan (CT scan slice thickness recommended to be no greater than 5 mm). At baseline and in follow-up, only the short axis will be measured and followed.

Non-measurable disease. All other lesions (or sites of disease), including small lesions (longest diameter <10 mm or pathological lymph nodes with ≥ 10 to <15 mm short axis), are considered non-measurable disease. Bone lesions, leptomeningeal disease, ascites, pleural/pericardial effusions, lymphangitis cutis/pulmonitis, inflammatory breast disease, and abdominal masses (not followed by CT or MRI), are considered as non-measurable.

Note: Cystic lesions that meet the criteria for radiographically defined simple cysts should not be considered as malignant lesions (neither measurable nor non-measurable) since they are, by definition, simple cysts.

‘Cystic lesions’ thought to represent cystic metastases can be considered as measurable lesions, if they meet the definition of measurability described above. However, if non-cystic lesions are present in the same patient, these are preferred for selection as target lesions.

Target lesions. All measurable lesions up to a maximum of 2 lesions per organ and 5 lesions in total, representative of all involved organs, should be identified as target lesions and recorded and measured at baseline. Target lesions should be selected on the basis of their size (lesions with the longest diameter), be representative of all involved organs, but in addition should be those that lend themselves to reproducible repeated measurements. It may be the case that, on occasion, the largest lesion does not lend itself to reproducible measurement in which circumstance the next largest lesion which can be measured reproducibly should be selected. A sum of the diameters (longest for non-nodal lesions, short axis for nodal lesions) for all target lesions will be calculated and reported as the baseline sum diameters. If lymph nodes are to be included in the sum, then only the short axis is added into the sum. The baseline sum diameters will be used as reference to further characterize any objective tumor regression in the measurable dimension of the disease.

Non-target lesions. All other lesions (or sites of disease) including any measurable lesions over and above the 5 target lesions should be identified as non-target lesions and should also be recorded at baseline. Measurements of these lesions are not required, but the presence, absence, or in rare cases unequivocal progression of each should be noted throughout follow-up.

